***This is a work copy!***  
**3M Restricted**

 
3M Deutschland GmbH [name] [name], Germany
	
Clinical Investigational Plan / Protocol
 
3M Confidential
	
CLIN-PROT-EU-05-293312 Version: 3 Status: Release Release Date: 01/30/2018 07:29:52 AM CST Page 38 of 60

--	--	---

4. Timekeeper stops stopwatch when nurse indicates product application is finished
5. Weigh the skin protectant building up the moisture barrier if the patient is allocated to the IAD hospital standard care group (content in gram after application)

IAD Skin Assessment

Ghent Global IAD Categorization Tool [33]

The study nurses will conduct daily skin assessments to determine the IAD severity category according to the GLOBIAD Tool definitions (appendix 24.2):

IAD 1A: persistent redness without clinical signs of infection

IAD 1B: persistent redness with clinical signs of infection

IAD 2A: skin loss without clinical signs of infection

IAD 2B: skin loss with clinical signs of infection

IAD free: skin free of any IAD signs, including erythema

The IAD severity category is to be documented in the IAD study diary.

The study nurses will receive a training regarding the GLOBIAD Tool at start of study.

In addition, the nurses will be trained in signs of infection and how to discriminate Incontinence-associated dermatitis from pressure ulcers.

Measurement Sheet to estimate the IAD affected area

The measurement sheet provided by the sponsor will be used on a daily basis to estimate the total area affected by IAD inclusive signs of erythema and in addition the area that is affected by skin loss only (skin is moist, as the epidermal layer is missing). The predefined markings of the measurement sheet will help to provide a rough estimate and to determine the cm^2 cluster range for the study documentation. All areas with IAD signs inclusive erythema or of skin loss will be summed up for the front and back side separately. The measurement sheet is to be used without contact to patient's skin.

Blinded IAD skin assessment based on photographs

All study nurses will receive an intensive training in digital photography to ensure consistent picture quality throughout the study. The nurses will take the pictures according to the instructions of the site procedure manual. The central reader will conduct a blinded skin assessment according to the independent review manual and evaluate up to four photo documentation time points per patient depending on his/her IAD severity category beginning of the study. The following photo documentation will be assessed by the central reader

 3M Deutschland GmbH [name] [name], Germany	Clinical Investigational Plan /  Protocol  3M Confidential	CLIN-PROT-EU-05-293312 Version: 3 Status: Release Release Date: 01/30/2018 07:29:52 AM CST Page 39 of 60
--	--	---

according to the independent review manual:

- (1) Photos at the start of the study (Day 01)
- (2) Photos to confirm the endpoint of 100% re-epithelialization of IAD 2 lesions for patients that started with skin loss beginning of the study (first time)
- (3) Photos to confirm the complete healing endpoint (first time; skin free of any IAD signs, including erythema)
- (4) Photos at the end of the study (Day 21 or discontinuation)

The photos for the above mentioned study relevant time points will be uploaded into a photo database that enables centralized independent blinded assessor review.

All other photos taken on Day 04, 07, 10, 13, 16, 19 will be used as back-up photos for the study. The back-up photos are to be kept on the SD memory cards and stored in the IAD Study Diary. The blinded skin assessor will categorize the severity of IAD according to the GLOBIAD Tool. In addition, the blinded skin assessor will trace the area affected by IAD inclusive signs of erythema and the area affected by skin loss only. The software will calculate the area in cm^2 based on the tracing information. At the start of the study the blinded skin assessor will receive a training with regard to the tracing procedure, photography database and software.

#### IAD Care Assessment

The study nurses together with the ward nurses will collect the information needed to calculate the material cost based on product utilization, application frequency and days of treatment in the IAD study diary. On a daily basis the nurses will track the following information for each day stayed in the hospital during the study participation (day & night): incontinence status continued/discontinued, presence of urinary catheter or fecal management system, number of absorbent pad or diaper changes, number of intimate cleansing procedures, number of applications regarding Cavilon Advanced Skin Protectant or local IAD care products and number of IAD related visits of specialists. In addition, the IAD care products will be specified in more detail in the eCRF providing information such as product name, treatment duration period, product type, manufacturer, REF number (indicates the manufacturer's catalogue number so that the medical device can be identified), packaging unit, number of containments used for the study. The study nurses will receive a training how to document the information at the start of the study.

 
3M Deutschland GmbH [name] [name], Germany
	
Clinical Investigational Plan / Protocol
 
3M Confidential
	
CLIN-PROT-EU-05-293312 Version: 3 Status: Release Release Date: 01/30/2018 07:29:52 AM CST Page 40 of 60

--	--	---

## 12. Monitoring

The present study is an international study with study sites in different European countries. Sites will be initiated in a site initiation visit. On-site monitoring visits will be conducted by sponsor or CRO authorized personnel as frequently as necessary. Monitors will record dates of the visits in a study site visit log that will be kept at the study site.

During monitoring visits, monitors will compare the data entered into the eCRFs with source documents such as the hospital or clinic records and the IAD study diary. The nature and location of all source documents will be identified to ensure that all sources of original data required to complete the eCRF are known to the sponsor and study-site personnel and are accessible for verification by the sponsor study-site contact. If electronic records are maintained at the study site, the method of verification will be discussed with the study-site personnel.

No audits are planned for the present study. The sponsor reserves the right to carry out audits if deemed necessary. Sites will be informed about the audit no less than 2 weeks prior to the audit. The institutions (sites), the investigators and the participating patients have to agree to give monitors, auditors and inspectors (authorized persons) free access to the medical records of the study participants.

### 12.1 Source data

100% source data verification will be performed for patients' informed consent and key patient data. Details will be described in the Monitoring Manual. Throughout the study, sites will be monitored for patient enrolment.

Key monitoring activities at sites will comprise:

- Review and check of Investigator Site File for completeness and correctness (including positive ethics committee vote, list of EC participants, signature/delegation log, patient enrolment log, site staff qualification documentation)
- Check of signed and dated Informed Consent Form for every patient
- Check of eligibility of every patient
- Source data verification as specified in the Monitoring Manual
- Check of documentation of (S)AEs

Investigators agree to enable direct access to source documentation (medical records, IAD study diary) for the purpose of verifying data recorded in the eCRF for consistency with original source data. Findings from monitoring reviews of eCRFs and source documents will be discussed with the study-site personnel. The sponsor expects that, during monitoring visits, the relevant study-site personnel will be available, the source documentation will be

 3M Deutschland GmbH [name] [name], Germany	Clinical Investigational Plan / Protocol  3M Confidential	CLIN-PROT-EU-05-293312 Version: 3 Status: Release Release Date: 01/30/2018 07:29:52 AM CST Page 41 of 60
--	---	---

accessible, and a suitable environment will be provided for review of study-related documents.

## 13. Data management

### 13.1 Data review, database cleaning, data query management

Electronic Data Capture (eDC) will be used for this study. The study data will be transcribed by study-site personnel from the source documents into an electronic CRF, and transmitted in a secure manner to the sponsor/authorized CRO within the time agreed upon between the sponsor and the study site. The investigator's study file contains the source data location list. The investigator has to ensure accuracy, completeness and timeliness of the data reported in the eCRFs, in all required reports and in the investigator's study file. The investigator has to verify that all data entries in the eCRFs are accurate and correct.

Reportable events will be communicated to authorities and sites according to the sponsor's SOPs.

Data will be entered into a validated electronic CRF using the authorized CRO's certified electronic data capture (eDC) system. Programmed data cleaning checks will be used in addition to manual review to check for discrepancies and to ensure consistency of data. An electronic audit trail system will be maintained within the system to track all changes in the database once the data have been saved into the system. Regular backups of the electronic data will be performed. Furthermore, the CRO authorized personnel will regularly review eCRFs for accuracy and completeness during on-site monitoring visits and after transmission to the sponsor. Discrepancies will be resolved with the investigator or designee, as appropriate.

All site-related eCRF entries, corrections, and alterations must be made by the investigator or other authorized study-site personnel. If necessary, queries will be generated in the eDC tool. If corrections to data are needed after the initial entry in the eCRF, this can be done in either of the following ways:

- Investigator and study-site personnel can make corrections in the eDC tool at their own initiative or as a response to an auto query generated by the eDC tool.
- Sponsor or sponsor delegate can generate queries for resolution by the investigator and site personnel.

Any change or correction to the eCRF after first entry and saving must be accompanied by a reason for the change. Corrections made after the investigator's review and signing (by

 
3M Deutschland GmbH  [name]  [name], Germany
	
Clinical Investigational Plan /  Protocol
 
3M Confidential
	
CLIN-PROT-EU-05-293312  Version: 3  Status: Release  Release Date: 01/30/2018  07:29:52 AM CST  Page 42 of 60

--	---	--

means of a password/electronic signature) of the completed eCRF will have to be reapproved by the investigator. The investigator will have to maintain a list of personnel authorized to enter data into the eCRF.

### **13.2 Verification, validation and securing of eDC system**

The certified eDC system used for the study database integrates numerous functions from the areas of electronic data capture, double-data-entry and data management in one application with centralized data storage. The system complies with all relevant GCP and FDA regulations, in particular with 21 CFR Part 11 offering a full audit trail, user and role management with electronic signatures. Data storage is secure and data are accessible to authorized personnel, only.

### **13.3 Data retention and archiving**

In compliance with ICH/GCP guidelines, the investigator/ institution will maintain all eCRFs and all source documents that support the data collected from each patient, as well as all study documents, Essential Documents for the Conduct of a Clinical Trial, and all study documents as specified by the applicable regulatory requirement(s). The investigator/institution will take measures to prevent accidental or premature destruction of these documents.

Study documents and materials have to be archived at investigator sites and at the sponsor's archive for no less than 10 years. Documents will be retained for a longer period if required by the applicable country regulatory requirements.

If the responsible investigator retires, relocates, or for other reasons withdraws from the responsibility of keeping the study records, custody must be transferred to a person who will accept the responsibility. The sponsor must be notified in writing of the name and address of the new custodian. Under no circumstance shall the investigator relocate or dispose of any study documents before having obtained written approval from the sponsor.

If it becomes necessary for the sponsor or the appropriate regulatory authority to review any documentation relating to this study, the investigator/institution must permit access to such reports.

 
3M Deutschland GmbH [name] [name], Germany
	
Clinical Investigational Plan / Protocol
 
3M Confidential
	
CLIN-PROT-EU-05-293312 Version: 3 Status: Release Release Date: 01/30/2018 07:29:52 AM CST Page 43 of 60

--	--	---

The sponsor will archive study documents and study data electronically and as paper versions.

#### **13.4 Notification requirements and time frames**

The study may be subject to auditing activities by appropriate regulatory authorities. It is important that the Investigator and relevant study personnel are available during audits/inspections and that sufficient time is devoted to the process. Data requested by regulatory authorities have to be provided within the required time frames.

#### **13.5 Corrective and preventive actions and principal investigator disqualification criteria**

The Investigator and respective study personnel will be trained by the sponsor and/or 3M authorized representatives on study documentation to ensure the accuracy and completeness of the data reported in the eCRFs and other documents such as study diaries. The site monitor will verify that study records are adequately maintained and address necessary corrective actions if needed. Submission of knowingly false information from the Investigator to 3M or failure to comply with the study protocol and applicable regulations will disqualify the Investigator from the study.

#### **13.6 Other aspects of clinical quality assurance**

3M and authorized CRO are responsible for implementing and maintaining quality assurance and quality control systems through written standard operating procedures to ensure that this study is conducted and data are generated, documented and reported, in compliance with the protocol, GCP and regulations. Study monitoring is carried out to accomplish this.

### **14. Deviations from clinical investigation plan**

#### **14.1 Amendments**

The party initiating an amendment must confirm it clearly in writing using the Amendment/Administrative Revision Form of the ethics committee if applicable. It must be signed and dated by 3M and, in the case of a significant amendment, the Investigator. A significant amendment means one that affects the safety, rights or welfare of patients, the scope of the study or scientific quality.

 3M Deutschland GmbH [name] [name], Germany	Clinical Investigational Plan / Protocol  3M Confidential	CLIN-PROT-EU-05-293312 Version: 3 Status: Release Release Date: 01/30/2018 07:29:52 AM CST Page 44 of 60
--	---	---

3M will submit significant protocol amendments to the Investigator for submission to the ethics committee. 3M will also notify the Investigator when a protocol amendment may be implemented.

#### **14.2 Protocol Deviations**

A protocol deviation is a departure from the protocol that will likely affect the safety, rights or welfare of patients, the scope of the clinical study or the scientific quality.

A protocol deviation is only for an individual patient. Each protocol deviation will be documented by completing a Protocol Deviation Case Report Form. This documentation will include the type of deviation and a description of the circumstances surrounding the deviation.

#### **15. Device accountability**

3M requires investigators to maintain accountability and adequate inventory security of the study device at all times. The investigator or designee will:

- Upon receipt of study device, check the contents and return the completed confirmation of receipt to the sponsor.
- Keep study device in a secure storage area, accessible only to authorized individuals.
- Dispense study device only to patients properly enrolled into the study.
- Return all unused study device to 3M at the end of the study, or dispose of as agreed upon.

#### **16. Statement of compliance**

This study will be conducted in accordance with the ethical principles that have their origin in the Declaration of Helsinki. All regional or national regulations will be followed, as appropriate. The study will not begin until the local Ethics Committees approved the study. Any additional requirements imposed by the Ethics Committees will be followed, if appropriate. The CE-marked study device will be used within its intended use. 3M recognizes its liability in law to compensate for any injuries sustained by patient participation in this study in accordance with the relevant guidelines of the countries where the study is conducted.

 3M Deutschland GmbH [name] [name], Germany	Clinical Investigational Plan / Protocol  3M Confidential	CLIN-PROT-EU-05-293312 Version: 3 Status: Release Release Date: 01/30/2018 07:29:52 AM CST Page 45 of 60
--	---	---

## 17. Informed consent process

The Investigator must ensure that written informed consent is obtained from the patient or patient's legally authorized representative before including any patient, and before conducting any study-related assessments. Informed consent may be given by the legally authorized representative only if a patient is unable to make the decision to participate in the study (e.g. seriously ill or unconscious patient, mentally ill person, mentally handicapped person). In such cases, the patient shall also be informed about the clinical study within his/her ability to understand. The Investigator must provide the prospective patient or the prospective patient's legally authorized representative, with sufficient opportunity to consider whether or not to participate, and minimize the possibility of coercion or undue influence. The process is designed to 1) give the patient and/or legally authorized representative all the information that he/she needs, 2) ensure that the patient and/or legally authorized representative understands the information and 3) give the patient and/or legally authorized representative a chance to consider study participation. The process should permit the patient and/or patient's legally authorized representative to ask questions and exchange information freely. Specifically, the Investigator is to explain to each patient and/or patient's legally authorized representative all elements of informed consent. After the explanation, the patient or legally authorized representative will voluntarily sign and date the consent/assent form if they wish to participate in the study. A copy of the consent/assent form must be provided to the patient or the patient's legally authorized representative. A signed and dated copy of the consent/assent form must be maintained in the Investigator Site File at all times. The informed consent process must be followed, and the patient's participation in the study, must be documented in the patient's medical record/chart.

### 17.1 Special circumstances for informed consent

#### 17.1.1 Patient needing legally authorized representatives

Informed consent process is to be followed as described under 17.

#### 17.1.2 Patient unable to read or write

If patient is unable to read or write an independent witness must be present throughout the process. The written informed consent form and any other information must be read aloud and explained to the prospective study participant or his/her legally authorized representative and, whenever possible, either must sign and personally dated the

 3M Deutschland GmbH [name] [name], Germany	Clinical Investigational Plan /  Protocol  3M Confidential	CLIN-PROT-EU-05-293312 Version: 3 Status: Release Release Date: 01/30/2018 07:29:52 AM CST Page 46 of 60
--	--	---

informed consent form. The witness also signs and personally dates the informed consent form attesting that the information is accurately explained and that informed consent is freely given.

## 18. Adverse events, adverse device effects and device deficiencies

### 18.1 Assessment of safety

The study assesses the effects of a CE-marked device used within its intended use in comparison to hospital IAD standard care. Following the guidance of MEDDEV 2.12 rev 8 “Guidelines on a medical devices vigilance system” all incidents will be assessed and reported according to the reporting modalities of the national competent authorities. The national regulations and local requirements for clinical studies with CE-marked device will determine which safety issues are to be reported to the ethics committees/institutional review boards. Beside the regulatory framework, the sponsor defines the following safety documentation for this study: The principal measure of safety will be the occurrence and nature of serious adverse events probably or possibly related to the study device (i.e. serious adverse device effects) or hospital IAD care products used in this study. Additionally, all adverse events probably or possibly related to the study device (i.e. adverse device effects), the hospital IAD care products or the study procedures will be documented. Adverse events with direct effect on the skin assessment area are of interest and will be documented as well. Deficiencies of the study device with respect to its identity, quality, durability, reliability, safety or performance including malfunctions, use errors, and inadequate labelling are to be documented on a sponsor provided device deficiency form but not in the eCRF (meaning quality complaints and near incidents of the study device). This includes any discovery or malfunction or deterioration in the characteristics and/or performance of the study device, as well as any inadequacy in the labelling or in the instructions for use which might have led to a deterioration in the state of health of patient or user if the circumstances would have been less fortunate or the event would not have been prevented due to the timely intervention of health care personnel (all device deficiencies that led to any hazard for the patient have to be regarded as adverse device effect and are to be documented in the eCRF).

NOTE: Untoward medical occurrence, unintended disease or injury or any untoward clinical signs (including an abnormal laboratory finding) in patients, users or other persons that are not linked to the products or procedures used in this study or do not directly affect the skin

 3M Deutschland GmbH [name] [name], Germany	Clinical Investigational Plan / Protocol  3M Confidential	CLIN-PROT-EU-05-293312 Version: 3 Status: Release Release Date: 01/30/2018 07:29:52 AM CST Page 47 of 60
--	---	---

assessment area are to be excluded from documentation including all internal diseases unless local regulations provide for this.

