#### 18.1.1 Safety parameters

The main safety parameters of this post-market IAD care study are the number and nature of serious adverse events possibly or probably related to the study device (i.e. serious adverse device effects) or to the IAD care products used in the comparative group.

Additionally, the number and nature of the following adverse events will be documented:

- adverse events probably or possibly related to the study device (i.e. adverse device effects)
- adverse events probably or possibly related to one of the IAD hospital care products
- adverse events probably or possibly related to one of the study procedures
- adverse events with direct effect on the skin assessment area. Examples are pressure ulcers or skin infections such as fungal/bacterial/viral infections within the skin area observed for this study.

All national and local requirements with regard to safety documentation will be considered for this study. Adverse events not mentioned in the list above will not be collected/analyzed during this study.

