### Adverse Event

Any untoward medical occurrence, unintended disease or injury, or any untoward clinical signs (including abnormal laboratory findings) in subjects, users or other persons, whether or not related to the investigational medical device.

NOTE 1: This definition includes events related to the investigational medical device or the comparator.

NOTE 2: This definition includes events related to the procedures involved.

NOTE 3: For users or other persons, this definition is restricted to events related to investigational medical devices.

 3M Deutschland GmbH [name] [name], Germany	Clinical Investigational Plan / Protocol  3M Confidential	CLIN-PROT-EU-05-293312 Version: 3 Status: Release Release Date: 01/30/2018 07:29:52 AM CST Page 49 of 60
--	---	---

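### The exclusion NOTE in 18.1 joins two negatives with *or*, so read literally it tells sites not to record events that 18.1 and 18.1.1 require

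*Combined protocol and SAP*

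**What the plan says.** The body of 18.1 gives two separate grounds for documentation. The first is relatedness: "all adverse events probably or possibly related to the study device (i.e. adverse device effects"), and likewise events related to "the hospital IAD care products or the study procedures will be documented". This ground has no limit on location. The second is location: "Adverse events with direct effect on the skin assessment area are of interest and will be documented as well". This ground has no limit on causality.

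Section 18.1.1 repeats both grounds as a four-item list. On the skin-area item it adds: "Examples are pressure ulcers or skin infections such as fungal/bacterial/viral infections within the skin area observed for this study". It closes by saying that events not on the list are neither collected nor analysed.

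The NOTE at the end of 18.1 states an exclusion. It covers untoward occurrences "that are not linked to the products or procedures used in this study or do not directly affect the skin" and, after the page break, "assessment area are to be excluded from documentation including all internal diseases unless local regulations provide for this".

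**The concern.** The NOTE should be the mirror image of the inclusion rule, and as worded it is not. Each half has its own verb and its own negative, so an event is excluded as soon as one half applies. A site can follow the NOTE in good faith and still breach 18.1.1.

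This matters for endpoint 11 in 7.3, the number and percentage of patients with adverse events. The synopsis ties that endpoint to adverse events as this study defines them. Chapter 18 supplies the definition, and it gives two answers. The schedules in 24.1 mark adverse events only as recorded if applicable, so they do not settle which rule holds. With three sites in three countries, different readings would mean pooling counts collected under different rules.

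The skin-area item is also the only ground in 18.1.1 that needs no judgement of causality. The literal NOTE would make every event depend on that judgement, in a study where 7.2 says the study nurses cannot be blinded.

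**Working it through.** The plan gives no figure to reproduce here. The check sets the rules side by side.

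Let A mean that the event is related to a study product or procedure, and B that it directly affects the skin assessment area.

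- 18.1 (body) and 18.1.1 (list): document if A or B.
- NOTE in 18.1, as worded: exclude if (not A) or (not B). What remains is A and B.
- 18.1.1 (closing rule): exclude only what is off the list, that is (not A) and (not B).

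| Event | 18.1 and 18.1.1 | NOTE, literal | Agree? |
|---|---|---|---|
| A and B | document | document | yes |
| A, not B | document | exclude | **no** |
| not A, B | document | exclude | **no** |
| not A, not B | exclude | exclude | yes |

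The rules conflict in 2 of 4 cells. If the NOTE excluded only (not A) and (not B), it would be the exact complement of A or B, and all 4 cells would agree.

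**Cell A, not B: related, outside the area.** The synopsis extends skin assessment to the region from navel to upper thigh, back and front, so the area is wider than the treated study area. Section 10 confines device application to the study area and, where IAD is visible, the genital area and frontal skin folds. Local reactions will therefore mostly fall inside the assessed area. What is left is mainly reactions elsewhere on the body. Allergic reaction is the only anticipated device effect (4.2, 18.2), and the text does not confine it to treated skin. For serious related events, 18.4.4 requires a report to the sponsor within 24 hours and entry on the Adverse Event Form, with no location limit. The exposed events are thus mainly non-serious ones. Section 18.4.4 is also a further text that the literal NOTE contradicts.

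**Cell not A, B: unrelated, inside the area.** Two other records catch part of this cell. Section 9.3 documents withdrawals for pressure ulcers of stage III, IV or unstageable and for infections needing topical treatment, and records them as adverse events if applicable. The daily skin assessment in 11.2 separates categories with and without signs of infection. Neither route catches a stage II pressure ulcer judged unrelated. A GLOBIAD category in the diary is also not an adverse event record.

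**Sensitivity of endpoint 11.** With 60 patients allocated 1:1 there are 60 / 2 = 30 per arm. One patient whose only event falls in a disputed cell moves that arm's percentage by 1 / 30 = 3.3 percentage points. Within one IAD stratum there are 30 / 2 = 15 per arm, and the shift is 1 / 15 = 6.7 points. The documents give no expected frequency for such events, so these are shifts per patient and not a forecast.

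**The case against.** The best reply is that only one reading is coherent. Taken literally, the NOTE cancels sentences a few lines above it, and 18.1.1 follows with an explicit list and a closing rule. A sensible site would read the NOTE as covering events that meet neither condition, and would take internal diseases to mean unrelated ones. Under 12.1, monitors also check adverse event documentation. This stands as far as intent goes: it makes the NOTE a drafting error and not a deliberate narrowing. It does not make the text safe, because the NOTE is a direct instruction not to record, and nothing says that 18.1.1 takes precedence.

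Three stronger readings are tempting, and the documents do not support them.

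- A reader might infer that serious device reactions away from the treated skin would be lost, and with them the principal safety measure. Section 18.4.4 captures related serious events independently. Sections 18.1 and 18.1.2 also require device deficiencies that led to a hazard for the patient to be entered as adverse device effects.
- A reader might infer that device-related events in nurses or other users distort endpoint 11, because the NOTE mentions users and the definition in 18.3 includes them ("For users or other persons, this definition is restricted to events related to investigational medical devices"). Endpoint 11 counts patients, and 18.1.2 collects safety parameters for study participants, so user events cannot change that percentage.
- A reader might take the table to mean that two thirds of recordable events are lost. It counts logical cells, not events.

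**Conclusion.** The NOTE in 18.1 is wrong as written. It conflicts with 18.1 and 18.1.1 in 2 of 4 cells: (a) related events outside the skin assessment area, mainly non-serious ones, and (b) skin-area events judged unrelated, which other records capture only in part. The severity is moderate. It is an internal inconsistency in an operative recording rule, and its plausible effect is uneven recording for endpoint 11 between sites. It is not a loss of the principal safety measure.

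The conclusion about the text rests on the wording alone. The practical effect assumes that at least one site applies the NOTE literally and meets an event in a disputed cell. The documents allow neither to be quantified.

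**What to change.** Reword the NOTE so that it excludes only events meeting neither condition, for example: *Events that are neither related to a study product or study procedure nor directly affecting the skin assessment area are not documented.* Limit the reference to internal diseases to those meeting the same condition, and keep the proviso on local regulations. State the rule in site training, with one example from each disputed cell: a non-serious related reaction outside the area, and a pressure ulcer inside it judged unrelated.

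The cost is one protocol sentence, handled under the amendment procedure in 14.1, and one line of training. No data are needed beyond what 18.1.1 already asks for. The reworded NOTE then agrees with 18.1, 18.1.1 and 18.4.4.
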